# **Study Summary**

Title	Pitocin or Oral Misoprostol for PROM IOL in
	Nulliparous Women with Unfavorable Cervical
	Exams
Short Title	POM PROM
Methodology	Randomized trial
Study duration	24 Months
Study Center (s)	Single-center
Objective	To determine if Pitocin (oxytocin) or oral
	misoprostol results in a shorter interval to
	delivery after the start of induction in nulliparous
	women with unfavorable cervical exams with
	premature rupture of membranes (PROM).
Number of Subjects	155
Diagnosis and Main Inclusion Criteria	PROM ≥ 36 weeks gestation; Singleton gestation
	in vertex presentation; Cervix ≤ 2 cm dilated and
	Bishop < 8; No contraindication to vaginal
	delivery; No evidence of infection
Study Product (s), Dose, Route, Regimen	Oral Misoprostol – 50 mcg q4H
	IV Pitocin (Oxytocin) – 2 mU/min, increased by 2
	mU/min to achieve 4-5 contractions in 10
	minutes with cervical change. Max dose 40
	mU/min
Duration of administration	Oral Misoprostol – Max 6 doses or until cervical
	ripening and/or delivery has been achieved
	Pitocin – Until delivery
Primary Outcome	Time from IOL to delivery (hours)
Statistical methodology	Intention to treat analysis, chi-square test for
	categorical variables, two-sample t-test for
	continuous variables

# **1 BACKGROUND AND RATIONALE**

# 1.1 Condition Background

Premature rupture of membranes (PROM) occurs in approximately 8% of pregnancies at term. Although onset of spontaneous labor is often prompt after membrane rupture, a delay from PROM to labor is associated with an increased risk of intrauterine infection and its associated maternal and fetal complications. For this reason, ACOG endorses induction of labor for PROM "if spontaneous labor does not occur near the time of presentation."

#### 1.2 Rationale

The optimal method for PROM induction is less clear. Prior literature has examined the use of Pitocin (Oxytocin), vaginal and oral misoprostol, and dinoprost with mixed results. The TermPROM study found an increased risk of chorioamnionitis and NICU admission among women treated with vaginal misoprostol for induction.

The postulated link between vaginal misoprostol and chorioamnionitis is the need for vaginal examination for placement of the misoprostol; more vaginal examinations could potentially increase the risk for infection. Utilizing oral misoprostol would eliminate the need for a vaginal exam for administration, thereby potentially mitigating this risk of infection. Currently, vaginal and oral misoprostol as well as Pitocin (Oxytocin) are used routinely in clinical care based on provider discretion.

Among 7 randomized controlled trials examining the use of oral misoprostol as compared to Pitocin (Oxytocin), two found oral misoprostol to result in faster induction to delivery, two found Pitocin to result in faster deliveries, and the remaining two found no difference between the two. These studies are limited by small sample size, inadequate reporting of patient demographics, varied misoprostol and Pitocin (Oxytocin) protocols, and inconsistent primary outcomes. Therefore, the utility of oral misoprostol in this population has not been established. Furthermore, its efficacy in specific patient populations is unreported in the literature.

## 2 STUDY AIMS

## 2.1 AIM 1:

To determine if Pitocin (Oxytocin) or oral misoprostol results in a shorter interval to delivery after the start of induction among nulliparous women with unfavorable cervical exams with PROM.

## 2.2 Endpoints

#### 2.2.1 Primary Endpoint

Time (hours) from start of IOL to delivery

## 2.2.2 Secondary Endpoints

- Suspected intraamniotic infection (Defined as maternal fever plus 1 or more of maternal leukocytosis, purulent cervical drainage, or fetal tachycardia
- Time (hours) from PROM to delivery
- Time (hours) from IOL to vaginal delivery
- Time (hours) from PROM to vaginal delivery
- Cesarean delivery
- Composite maternal outcome

- Postpartum hemorrhage, blood transfusion, endometritis, wound infection, VTE, hysterectomy, ICU admission, readmission within 4 weeks, death
- Composite neonatal outcome
  - ICN adm > 48 hours, neonatal blood transfusion, HIE, IVH grade
    3 or 4, headcooling, severe RDS, NEC, Sepsis, Death
- Patient satisfaction as measured by Birth Satisfaction Scale- Revised (BSS-R)

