#### **3 PATIENT ELIGIBILTY**

Subjects must meet all of the inclusion and exclusion criteria to be enrolled to the study. Study treatment may not begin until a subject is consented and randomized.

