#### 3.1 Inclusion Criteria

**English-speaking** 

≥ 18 years of age

PROM ≤24 hours with no evidence of labor

PROM - Standard clinical diagnosis

Labor – >3 painful contractions in a 10 minute period, averaged over 30 minutes

≥ 36 weeks gestation

Agreeable to induction of labor

Singleton pregnancy

Vertex presentation

Cervical dilation ≤ 2 cm and Bishop score < 8

Exam done by senior resident, fellow, midwife or attending to confirm eligibility

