## 7.1 Sample Size and Accrual

The sample size is based on the mean time to delivery with Pitocin(oxytocin) after PROM IOL of 10.4 hours, with a standard deviation of 4.3 hours. For a power of 80% and an alpha of 0.05, 148 women would be needed to find a 2-hour difference in time to delivery. To account for drop out, we plan to enroll 155 women.

We estimate 15-20 eligible women deliver at HUP per month. We anticipate approaching 80% of these women or approximately 14 per month. With an estimated 50% consent rate, we would enroll approximately 7 women per month. Therefore, we would need 24 months to reach our target enrollment of 155 women.

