## 7.2 Data Analyses Plans

Measures of relative risk will include 95% confidence intervals. Descriptive statistics will be presented as mean with standard deviation, median with interquartile range, or proportion with 95% confidence interval based on data type and distribution. Comparisons between groups will be performed using a Chi-square or Fisher's exact test for categorical variables and parametric or non-parametric tests for continuous variables, as appropriate. Intention-to-treat analyses will be conducted such that all patients with available follow-up measures will be included in the analysis. Statistical analyses were conducted in STATA, version 12.0 (College Station, Texas). Two-tailed P values of <0.05 will be considered statistically significant.

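### Time from PROM to delivery includes up to 24 hours fixed before randomisation, and the planned unadjusted comparison gives up precision on this secondary endpoint

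*Combined protocol and SAP*

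**What the plan says.** Section 2.2.2 of the combined protocol and SAP has two endpoints timed from membrane rupture: "Time (hours) from PROM to delivery" and "Time (hours) from PROM to vaginal delivery". The primary endpoint in section 2.2.1 starts later: "Time (hours) from start of IOL to delivery".

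Section 3.1 sets the entry window as "PROM ≤24 hours with no evidence of labor". Section 3 adds that "Study treatment may not begin until a subject is consented and randomized", so all time before randomisation is untreated.

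For analysis, the Study Summary names a "two-sample t-test for" continuous variables, and section 7.2 allows "parametric or non-parametric tests for continuous variables, as appropriate". Neither place names a covariate. Section 5.2 mentions no stratification by time since rupture.

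The sample size in section 7.1 ("148 women would be needed to find a 2-hour difference in time to delivery") rests on a mean of 10.4 h and an SD of 4.3 h for time to delivery after induction. It concerns the primary endpoint. No target difference or power is stated for the endpoints timed from PROM.

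**The concern.** For each woman, PROM-to-delivery time is the sum of two parts: the hours from rupture to randomisation, which are settled before any study drug is given, and the hours from randomisation to delivery, which treatment can change. An unadjusted comparison of the sum carries the variance of the first part into the standard error, although that part holds no information about treatment.

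If women enter at widely different times after rupture, the confidence interval may be too wide to be useful, and a null result could be misread as evidence that treatment does not affect the total duration of ruptured membranes. Section 1.1 gives delay after PROM as the infection concern, so the endpoint has a clinical purpose and deserves a usable interval. The first part is a baseline value, so its variance can be removed by adjustment without changing the mean difference being estimated.

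**Working it through.** **Inputs from the documents.** SD of induction-to-delivery time 4.3 h, difference 2 h, power 80%, alpha 0.05, 148 women (section 7.1); two-sided testing (section 7.2); entry 0 to 24 h after PROM (section 3.1).

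**Assumptions.** Allocation is 1:1 (the ratio is not stated), giving 74 per arm. The SD of the PROM-to-randomisation interval, *s*, is not given, so a range is shown. That interval is taken as independent of the later one. Randomisation-to-delivery time is given the SD of 4.3 h that section 7.1 states for induction to delivery.

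**Step 1: the plan's own figure.** A two-sided two-sample t-test with difference 2, SD 4.3, alpha 0.05 and power 80% needs 73.5 per arm. That rounds up to 74, or 148 in total, as in section 7.1. Power at 74 per arm is 80.2%.

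**Step 2: unadjusted PROM to delivery.** Endpoint SD = √(4.3² + s²). The 95% CI half-width = 1.976 × SD × √(2/74) = 0.325 × SD. Power is for an illustrative 2-hour difference.

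| Assumed s (h) | Endpoint SD (h) | Share of variance from s | 95% CI half-width (h) | Power |
|---|---|---|---|---|
| 0 | 4.30 | 0% | 1.40 | 80% |
| 1 | 4.41 | 5% | 1.43 | 78% |
| 2 | 4.74 | 18% | 1.54 | 72% |
| 3 | 5.24 | 33% | 1.70 | 64% |
| 4 | 5.87 | 46% | 1.91 | 54% |
| 5 | 6.59 | 57% | 2.14 | 45% |
| 6.93 | 8.15 | 72% | 2.65 | 32% |

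The last row is entry spread evenly over the window: 24/√12 = 6.93 h. It is a wide scenario that the criterion permits, not one that the documents describe.

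**Step 3: adjusted PROM to delivery.** Write Y = X + Z, with X the PROM-to-randomisation interval and Z the time from randomisation to delivery. A linear model of Y on arm and X leaves a residual SD of 4.3 h under independence, whatever *s* is, so the half-width is about 1.40 h. In 10,000 simulated trials with gamma-distributed Z and X uniform on 0 to 24 h, power for 2 h was 32% unadjusted and 79.6% adjusted.

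**Step 4: error rate.** In the same simulation with no treatment difference, the rejection rate was 4.9% unadjusted and 5.0% adjusted. The chance of a between-arm imbalance in X of 2 h or more is 0.01% at s = 3, 0.2% at s = 4, 1.5% at s = 5 and 7.9% at s = 6.93. The unadjusted standard error already allows for it.

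**Step 5: dependence between the parts.** With correlation ρ between X and Z, the unadjusted variance is 4.3² + s² + 2ρ(4.3)s and the adjusted residual variance is 4.3²(1 − ρ²). The first exceeds the second by (s + 4.3ρ)², which is never negative. At ρ = −0.3, unadjusted power is 78% at s = 3 and 41% at s = 6.93. At ρ = +0.3 it is 53% and 26%. So the gain depends on ρ, but apart from one degree of freedom adjustment does not lose precision.

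**Step 6: what the adjusted contrast is.** Because X is in the model, regressing Y = X + Z on arm and X gives the same arm coefficient and standard error as regressing Z on arm and X. The adjusted result is therefore the adjusted difference in randomisation-to-delivery time.

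**The case against.** A reader might infer that these hours undermine the trial's main comparison. They do not: the 2-hour difference, the SD of 4.3 h and the 148 women all belong to the primary endpoint, which starts at induction and contains none of them. The 80% in the table is a reference point, not a power that the plan claims for PROM to delivery.

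A reader might also infer that an unadjusted difference could be an artefact of one arm presenting later. In a single trial a chance imbalance can shift the estimate, but the interval is fixed before randomisation and balanced in expectation, and the test keeps its 5% error rate. The loss is one of precision.

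Nor do the documents show that the loss is large. With a spread of 1 to 2 h, power is still 78% to 72%, and the interval supplies more than half the variance only if its SD exceeds 4.3 h. Section 1.1 describes labour as often prompt after rupture and cites guidance favouring early induction, and section 3.1 excludes women in labour. None of this points to an even spread over 24 hours.

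The strongest objection is that adjustment turns the endpoint into randomisation to delivery. That differs from the primary only by the gap between randomisation and the start of treatment, so the regained precision is essentially the primary's own. This stands and should be stated openly. The unadjusted endpoint also describes the total duration of ruptured membranes, which is worth reporting. Neither point makes an unadjusted test the better way to estimate the treatment difference.

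Two smaller points also stand. Section 5.3 records the time of first dose or infusion start, but no section says that the time of randomisation is kept. And a fixed linear model needs protection if delivery times are skewed.

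**Conclusion.** The point holds as a minor loss of precision on a secondary endpoint. PROM to delivery includes up to 24 h that treatment cannot change, and the plan names only comparisons without covariates. Over assumed SDs of 1 to 6.9 h, with independence and 74 per arm, the unadjusted half-width is 1.43 to 2.65 h against about 1.40 h adjusted. Power for an illustrative 2-hour difference is 78% to 32% against about 80%. Where in that range the trial will fall cannot be told from the documents. There is no bias, no inflation of type I error and no effect on the primary endpoint.

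These figures do not carry over to PROM to vaginal delivery. The handling of cesarean deliveries is not stated, so the number of women analysed and the quantity estimated there are unknown.

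**What to change.** In section 7.2:

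- State that PROM to delivery is compared by a linear model with arm and the PROM-to-randomisation interval (hours) as a baseline covariate, with robust or bootstrap standard errors if times are skewed. Report the adjusted difference with its 95% CI.
- State that this contrast equals the one for randomisation to delivery adjusted for the same interval, so it closely tracks the primary and is not independent support for it.
- Keep unadjusted PROM-to-delivery summaries by arm as a description of total duration of ruptured membranes.
- Report the PROM-to-randomisation interval by arm in the baseline table.

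The same covariate can be used for PROM to vaginal delivery once the handling of cesarean deliveries is stated.

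The cost is a few sentences, with no extra patients or procedures and no change to endpoint definitions. Time of rupture is already needed for eligibility and for the endpoint. The sponsor should confirm that the time of randomisation is retained.

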#### **3 PATIENT ELIGIBILTY**

Subjects must meet all of the inclusion and exclusion criteria to be enrolled to the study. Study treatment may not begin until a subject is consented and randomized.

#### 3.1 Inclusion Criteria

**English-speaking** 

≥ 18 years of age

PROM ≤24 hours with no evidence of labor

PROM - Standard clinical diagnosis

Labor – >3 painful contractions in a 10 minute period, averaged over 30 minutes

≥ 36 weeks gestation

Agreeable to induction of labor

Singleton pregnancy

Vertex presentation

Cervical dilation ≤ 2 cm and Bishop score < 8

Exam done by senior resident, fellow, midwife or attending to confirm eligibility

## 3.2 Exclusion Criteria

Contraindication to misoprostol (Prior Cesarean section, prior uterine surgery)

Other contraindication to vaginal delivery

Intrauterine fetal demise

Major congenital anomaly

Chorioamnionitis at time of admission

36w-36w6d with unknown Group B Strep (GBS) status

#### 3.3 Vulnerable patient populations

Pregnant women are considered a vulnerable population. As the condition of interest is a

pregnancy-related and specific condition, it is unavoidable to exclude pregnant women from this research study. Oral misoprostol and Pitocin (Oxytocin) however, are currently used in clinical practice so the risks to this population are minimally increased from that experienced in routine clinical care.

Furthermore, neonates are considered a vulnerable population. We will be collecting data on neonates for our composite neonatal outcome. All risks to this vulnerable population will be less than minimal risk as it will involve chart review only after delivery. Subjects will be made aware that we will be collecting information on their neonates within the consent form.

## 3.4 Ensuring Necessary Medical Interventions

Enrollment in this study will alter the induction agent utilized after diagnosis of PROM. Continuous EFM and tocometry will occur on all patients in labor, consistent with standard of care. Mechanical cervical ripening will not be performed. The remainder of clinical care in labor will be at the covering OB providers' discretion. The frequency and timing of cervical examinations will occur per provider discretion. Standard treatment for GBS positive and GBS unknown patients will occur. The use of internal fetal monitoring and intrauterine pressure catheter will be at the discretion of the OB provider. Standard obstetric indications for cesarean delivery will be also be at the discretion of the OB provider.

## 3.5 Potential Benefit to Participants

Participation in this study is for research purposes and there is no direct health benefit to the subjects.

#### 4 TREATMENT ARMS

## 4.1 Treatment Dosage and Administration

- Oral Misoprostol 50 mcg q4H for up to 6 doses
  - Transition to Pitocin (Oxytocin) as determined by primary OB provider after cervical ripening is no longer indicated
- Pitocin (Oxytocin) The standard hospital protocol will be utilized. This regimen starts at a dose of 2 mU/min IV.
  - The dose is increased by 2 mU every 15 minutes until contractions q2-3 minutes apart resulting in cervical change.
  - The max dose is 40 mU/min.

#### 4.2 Toxicities

- There are no known toxicities with the doses of misoprostol and Pitocin(Oxytocin) that we are using. One known possible side effect of oral misoprostol is GI distress (nausea, vomiting, diarrhea). If this occurs, attempts will be made to treat these symptoms with antiemetics or antidiarrheals as needed. If unresponsive to treatment, the medication will be discontinued. All women receiving misoprostol will also be monitored for frequency of contractions. The medication will not be administered if contractions >3 per 10 minute period, averaged over a 30 minute period.
- All women receiving Pitocin (Oxytocin) will also be monitored for frequency of contractions. The dose will be titrated to prevent tachysystole and fetal distress as per current Hospital of UPenn protocol. If tachysystole or fetal distress develop, the medication will be discontinued and the condition managed per OB provider discretion. Medication can be restarted upon resolution of tachysystole or confirmation of fetal well-being.

#### 4.3 Concomitant Medications/Treatments

 No additional induction agents will be utilized in conjunction with misoprostol or Pitocin (Oxytocin).

## 4.4 Duration of Therapy

- Oral misoprostol can be continued until max dose has been reached or the primary OB provider has deemed cervical ripening is no longer indicated
- Pitocin (Oxytocin) can be continued throughout the course of labor as per current HUP guidelines.

## 4.5 Duration of Follow Up

Women/neonate dyads will be followed for the development of any maternal or neonatal complications through the duration of the postpartum hospital stay as well as for readmissions within four weeks of delivery.

# 4.6 Blinding

Due to the nature of the treatment arms, neither providers nor participants will be blinded to their treatment arm.

#### 5 STUDY PROCEDURES

#### 5.1 Screening for Recruitment and Recruitment Process

Women meeting the criteria listed in section 3.1 will be invited to participate in the study and written informed consent will be obtained from those who choose to participate.

## 5.2 Randomization

Eligible, consented women will be randomized via a random generated randomization scheme within RedCap. The randomization scheme will be generated by a statistical associate not involved in the study.

#### **5.3 Procedures During Treatment**

After randomization, the appropriate medication will be ordered in Epic by the covering clinician and obtained through inpatient pharmacy as is the current clinical practice. The resulting trial arm will be disclosed to the patient and the patient RN.

- For participants randomized to oral misoprostol, the RN will administer and record the time of first dose. Re-dosing of medication will occur per the schedule described in sections 4.1
- For participants randomized to Pitocin (Oxytocin), the RN will begin Pitocin (Oxytocin) infusion and record the time of infusion start. Dose adjustments will be made according to the clinical protocol described in section 4.1.

The remainder of clinical care in labor and delivery will occur as per primary OB provider's discretion as described in section 3.4.

## 5.4 Follow-up Procedures

During the postpartum hospital stay, women will be approached to complete a validated patient satisfaction survey, the BSS-R.

#### 5.5 Protections Against Physical Risk

There is minimal risk to the use of oral misoprostol or Pitocin(oxytocin) during labor. Both of these medications are currently employed in clinical use at the Hospital of the University of

Pennsylvania. A DSMB comprised of individuals who are not investigators on the trial will be utilized to monitor for adverse outcomes. A list of mandatory events that should be reported to the DSMB within 24 hours of occurrence will be supplied to all clinicians and research coordinators managing trial patients. Also all serious adverse events will be recorded and reported to the institutional review board.

#### 5.6 Protection against Loss of Privacy/Breech of Confidentiality

In order to protect a potential subject's privacy, study staff will only approach potential subjects in a private setting. Once consented, we will take multiple steps to protect the study subject from breach of confidentiality. The list linking the subject's name and medical record number will be kept behind the hospital firewall in a password-protected file. This file is only accessible through the hospital server to those individuals given password approval to access the file. Furthermore, the electronic database (REDCap) will be coded with a unique study identifier rather than with any individually identifiable private information. No PHI will be shared with anyone outside the institution.

#### 6 ADVERSE EVENTS

## 6.1 Adverse Event Monitoring

Adverse event data collection and reporting will be done to ensure the safety of subjects who will enroll be enrolled in thus study. Adverse events will be reported in a routine manner at scheduled times during the trial. Additionally, certain adverse events will be reported in an expedited manner to allow for optimal monitoring of patient safety and care.

All patients experiencing an adverse event, regardless of its relationship to study drug/device, will be monitored until:

- the adverse event resolves or the symptoms or signs that constitute the adverse event return to baseline;
- > any abnormal laboratory values have returned to baseline:
- there is a satisfactory explanation other than the study drug for the changes observed; or
- death.

